12.6 Protocol Amendment 3 Summary

Title: BOTOX® Treatment in Pediatric Upper Limb Spasticity: Open-label Study

Protocol 191622-105, Amendment 3

Date of Amendment: January 2014

Amendment Summary

This summary includes changes made to Protocol 191622-105 Amendment 2 (e-signature date 11 December 2012). [REDACTED]

[REDACTED]

[REDACTED]

Following is a summary of content-oriented changes that were made to each section of the protocol, and a brief rationale for these changes. Minor editorial and document formatting revisions have not been summarized.

Section(s)	Revision	Rationale
Title page	Referred to the Study Contacts Page for emergency telephone numbers; updated page 2	Per new Allergan protocol template
3.1	Changed “members” to “participants” and removed “or investigator” from the examples given of ad hoc SDRC participants	Clarification
Protocol Summary; 4.4	Modified Exclusion Criterion 11a regarding seizure frequency for exclusion Modified Exclusion Criterion 12 regarding vulnerable respiratory state Added Exclusion Criterion 27 to exclude patients with significant suicidality from treatment	Clarification Clarification To avoid confounding the safety data

Section(s)	Revision	Rationale
4.5.1	Added a sentence on use of anti-epileptics	Clarification that anti-epileptics are permissible during the study
5.4.4.1	Amended bullet (c) of the retreatment criteria	To specify that patients who experience certain adverse events will not receive further study treatments
5.4.5	Revised paragraph regarding retreatment for patients with adverse events of compromised respiratory function, aspiration, difficulty swallowing, or clinically significant excessive salivation	To specify that patients who experience these adverse events will not receive further study treatments
6.4	Added bullet that Allergan will supply a kilogram-only weight scale for selected sites, and that the site will supply it only if it is not already supplied by Allergan	To ensure that patient's weight is collected in kilograms only
9.3	Updated serious adverse event language	Per new Allergan protocol template
12.1.1	Amended second sentence regarding weight measurements	Clarification on requirements for weight measurements and that weight must be measured in kilograms
12.1.2	Added " temporal, rectal " to body temperature	As per common practices
12.1.13; 12.1.14	Amended "investigator" to "physician investigator"	Clarification

12.7 Protocol Amendment 4 Summary

Title: BOTOX® Treatment in Pediatric Upper Limb Spasticity: Double-blind Study

Protocol 191622-105, Amendment 4

Date of Amendment: July 2016

Amendment Summary

This summary includes changes made to Protocol 191622-105 Amendment 3 (January 2014). This protocol was amended to decrease the sample size.

Following is a summary of content-oriented changes that were made to each section of the protocol, and a brief rationale for these changes. Minor editorial and document formatting revisions have not been summarized.

Section(s)	Revision	Rationale
Title page	Updated Allergan medical safety physician and Allergan signatory information	Change in staff
Protocol Summary, 4.1 (Number of Patients)	Estimated number of patients to enroll in study was decreased from 350 to 213	Based on decreased number of completers from DBPC study due to adjusted treatment differences from upper limb studies.
Protocol Summary; 7.5 (sample size calculation)	Number of patients was revised from 350 to 213.	Based on decreased number of completers from DBPC study

NCT01603615

Study ID: 191622-105

Title: BOTOX® Treatment in Pediatric Upper Limb Spasticity: Open-label Study

Statistical Analysis Plan: 14 January 2019

**Allergan
Biostatistics
Analysis Plan**

Study ID: 191622-105

Study Title: BOTOX® Treatment in Pediatric Upper limb Spasticity: Open-label Study

Table of Contents

1.	Introduction.....	4
1.1	Primary Study Objectives and Design	4
1.2	Secondary and Other Objectives.....	5
2.	Analysis Populations and Data Conventions.....	5
2.1	Analysis Populations.....	5
2.3	Data Conventions	7
3.	Disposition and Exit Status.....	10
3.1	Disposition and Exit Status	10
4.	Demographics and Other Baseline Characteristics.....	10
4.1	Demographics	10
4.2	Concomitant Medications	10
5.	Efficacy Analyses	11
5.1	Collection of Primary Efficacy Measurement(s) and Derivation of Primary Efficacy Variable(s).....	11
5.2	Primary Efficacy Analyses	11
5.3	Secondary Efficacy Analyses.....	11
5.5	Subgroup Analyses for Efficacy Variables	13
6.2	Treatment Emergent Adverse Events	13

7. Interim Analyses	18
8. Pharmacokinetic Data Analyses	18
9. Health Outcomes Data Analyses	18
10. Data Collected but not Analyzed	18
11. Deviations from Protocol.....	18

1. Introduction

This analysis plan details the analyses that will be performed for BOTOX® (Botulinum Toxin Type A) Study 191622-105, an open-label study designed to evaluate the long-term safety of repeated doses of BOTOX for the treatment of pediatric upper limb spasticity.

There will be up to 5 treatments in the study. For the first treatment cycle, de novo patients (who did not participate in Allergan Study 191622-101) are to receive at least 6 U/kg and not to exceed 8 U/kg or 300 U in the affected upper limb (referred to as the study upper limb). Patients with clinically significant lower limb spasticity may be eligible to receive BOTOX treatment in affected lower limb(s). The combined upper and upper limb dose should not exceed 8 U/kg or 300U, whichever is lower.

Rollover patients (who participated in Allergan Study 191622-101), during the first treatment cycle may receive up to a maximum of 8 U/kg (not to exceed 300 U) in the same upper limb that was treated in Study 191622-101 (referred to as the study upper limb). Patients with clinically significant lower limb spasticity may be eligible to receive BOTOX treatment in affected lower limb(s) up to a maximum of 8 U/kg (not to exceed 300 U). The combined upper and lower limb dose should not exceed 8 U/kg or 300 U, whichever is lower, during the first cycle.

For treatment cycles 2 through 5, the maximum dose for the study upper limb only remains the same as in treatment cycle 1; the maximum dose for combined upper and lower limbs or for both lower limbs only for triplegic patients can be increased to 10 U/kg (not to exceed 340 U).

If a patient meets the retreatment criteria, including no indication of an unacceptable safety risk, and it is considered clinically appropriate by the investigator, the patient should receive at least 6 U/kg in the study upper limb every 12 to 14 weeks, with the total dose not to exceed the maximum specified for each treatment cycle.

Approximately 213 patients will be enrolled. The sample size was determined empirically rather than by sample size calculation.

1.2 Secondary and Other Objectives

[figure not shown]
There are no secondary or other objectives for this study.

2. Analysis Populations and Data Conventions

2.1 Analysis Populations

Safety data will be analyzed on the basis of all treated patients based on the treatment received, defined as the safety population.

2.3 Data Conventions

The data conventions and definitions listed in this section are to be applied to all analyses unless stated otherwise in a subsequent section of this Analysis Plan.

- Data will be analyzed according to the following treatment groups:
 - For rollover patients from Study 191622-101 under treatment group BTX 3 U/kg, BTX 6 U/kg, or Placebo, their corresponding treatment group will be

designated as BTX 3 U/kg/BTX, BTX 6 U/kg/BTX, or Placebo/BTX, respectively.

- For de novo patients, their treatment group will be designated as Placebo/BTX.
- Concurrent medication and prior medication will be calculated using the following convention: 1) If the stop date of taking medication is prior to first injection date, then it will be counted as prior medication; 2) If the start date of taking medication is after or on first injection date, then it will be counted as concomitant medication; 3) If the start date of taking medication is prior to first injection date and stop date is on or after last injection date, then it will be counted as both prior medication and concomitant medication.
- Concurrent procedures are defined as those taken on or after the first injection date.
- All data will be listed with the exceptions of commonly expected results such as physical examination, pregnancy tests results for females when not applicable, etc.
- Summary statistics of continuous variables will include the sample size (N), mean, standard deviation, median, minimum (Min), and maximum (Max).
- Summary statistics of categorical variables will include the sample size (N) and/or frequency counts and percentages.
- Medical Dictionary for Regulatory Activities (MedDRA) nomenclature will be used to code all adverse events (AEs) and medical history.
- World Health Organization Drug Dictionary Enhanced (WHO DDE) preferred name and MedDRA will be used to code all medications.
- Metric systems will be used for all applicable measures including (kg), height (cm), and clinical laboratory data (SI: Standard International units).
- Baseline is defined as the last non-missing observation prior to receiving the first treatment for de novo patients and the same baseline in study 191622-101 for the rollover patients. For some measurements not measured in study 191622-101, the last non-missing observation prior to receiving the first treatment in study 191622-105 will be used. Change from baseline is calculated as follow-up minus baseline value.
- Missing values will not be imputed.

- Study days from the treatment day of a certain treatment cycle will be calculated as:

Study days = visit date – most recent treatment day visit date + 1.

- The study day of an event that has occurred before first treatment day will be calculated as:

Study day = date of event – treatment 1 visit date.

- Partial dates occurring when calculation of study day is germane to the study outcome will be handled as follows:

If the year is missing then the date is treated as missing.

If either the month or the day is missing, then the closest to baseline possible will be used. That is, an event occurring the year before baseline would use December and/or the last day of the month. An event occurring the year after baseline would use January and/or the first day of the month.

All partial dates will be listed “as is” in the data listings.

- All adverse events (AEs) with missing onset dates will be identified and the missing dates will be imputed as follows for analysis. These imputations are only for assigning adverse events to a particular study phase; calculations such as days to onset will not use these imputations. All partial dates will be listed “as is” in the data listings.
 - (a) For AE onset date: If day and month are missing but year is available (..../yy) then the imputed day and month will be 01/01/yy or the injection date if they have the same year, whichever is later. If day is missing but the month and year are available (mm/../yy), then the imputed day will be mm/01/yy or the injection date if they have the same month and year, whichever is later.
 - (b) For AE stop date: If day and month are missing but year is available (..../yy) then the imputed day and month will be 12/31/yy or the study exit date if they have the same year, whichever is earlier. If day is missing but the month and year are available (mm/../yy), then the imputed day will be the last day of the month mm in the year yy or the study exit date if they have the same month and year, whichever is earlier.
 - (c) If the AE onset or stop month, day, and year are missing (..../..), then the study entry date will be used as the AE onset date and the exit date will be used as the AE stop date.

- Data from unscheduled visits or re-test visits will be treated the same way as scheduled visits, i.e., the dates of such visits will be used in the categorization of visit window. The algorithm handling multiple visits within a visit window will also be applied to unscheduled visits and re-test visits.
- There is no data pooling for efficacy analyses considering all are descriptive evaluations.
- The mean change from baseline for a given treatment group will be calculated by taking the sum of all individual changes from baseline divided by the number of patients with observations in that treatment group. As a consequence, patients without the particular follow-up data will not be taken into account, except if there is a missing value replacement method used.
- [REDACTED]

3. Disposition and Exit Status

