9.1 Definitions

9.1.1 Adverse Event

An adverse event is any untoward medical occurrence in a patient or clinical investigation subject administered a pharmaceutical product and that does not necessarily have a causal relationship with this treatment. An adverse event can therefore be any unfavorable and unintended sign (including an abnormal laboratory finding), symptom, or disease temporally associated with the use of a medicinal (investigational) product, whether or not related to the medicinal (investigational) product. In addition, during the screening period, adverse events will be assessed regardless of the administration of a pharmaceutical product.

Adverse events will be assessed and documented, as appropriate, throughout the study (ie, after informed consent has been obtained). At each visit, the investigator will begin by querying for adverse events by asking each patient/caregiver a general, non-directed question such as “How have you been feeling since the last visit?” Directed questioning and examination will then be done as appropriate. All reported adverse events will be documented on the appropriate eCRF.

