6.2 Treatment Emergent Adverse Events

Adverse events are collected for the period prior to the first treatment (which are referred to as pre-treatment AEs as cited in Section [Error! Reference source not found.](#)) and for the period on or after the first treatment.

An overall treatment-emergent adverse event (TEAE) is an adverse event with onset on or after the initiation of the first treatment or an adverse event with onset prior to the first treatment that worsened in severity or became serious on or after the initiation of the first treatment.

A treatment cycle treatment-emergent adverse event (TEAE) is an adverse event with onset on or after the initiation of the cycle treatment but before the initiation of the next cycle treatment, or an adverse event with onset prior to the cycle treatment that worsened in severity or became serious on or after the initiation of the cycle treatment but before the initiation of the next cycle treatment.

An AE that stops during certain treatment cycle and recurs in the subsequent treatment cycle(s) is considered as a TEAE in the subsequent treatment cycle(s) if it fulfills the TEAE definition above.

The number and percentage of patients reporting each event will be summarized by treatment cycle and overall as follows:

- i. By primary SOC and preferred term. At each level of summarization (overall, primary SOC, and preferred term) a patient will be counted once if he/she reports 1 or more experiences at that level.
- ii. By primary SOC, preferred term and severity. For a given adverse event of a patient, if more than 1 severity grade was reported, the worst severity grade will be included in the tabulation.

An overall summary of TEAE will be presented. In addition, individual patient data listings (including adverse event listings that include the investigator verbatim terms and MedDRA lower level terms) will be provided.

Furthermore, the assessment of possible distant spread of toxin will be performed using the list of 39 MedDRA preferred terms (version 19.0 or its updated version as appropriate during the time of data analysis).

MedDRA Preferred Terms Evaluated for Possible Distant Spread of Toxin

Cardiac Disorders

Bradycardia

Eye Disorders

Accommodation disorder
Diplopia
Extraocular muscles paresis
Eyelid function disorder
Eyelid ptosis
Pupillary reflex impaired
Vision blurred

Gastrointestinal Disorders

Constipation
Dry mouth
Dysphagia
Ileus paralytic

Infections and Infestations

Botulism

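### The SAP's rules for incomplete AE dates can put an event in the wrong study phase: rule (a) ignores a known stop date, and rule (c) relies on an undefined study entry date

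*SAP*

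**What the plan says.** SAP 2.3 (Data Conventions) gives three rules for AEs whose onset date is missing in whole or part. It says the imputed dates serve only to place an event in a study phase and are not used for days to onset.

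- **Rule (a), day missing:** "then the imputed day will be mm/01/yy or the injection date if they have the same month and year, whichever is later".
- **Rule (a), day and month missing:** the "imputed day and month will be 01/01/yy or the injection date if they have the same year, whichever is later".
- **Rule (c), everything missing:** "then the study entry date will be used as the AE onset date". The same sentence fills a missing stop with the date of exit, and its trigger is worded as a missing onset or stop.

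SAP 6.2 defines an overall TEAE as "an adverse event with onset on or after the initiation of the first treatment", or an earlier event that later worsened or became serious. A cycle TEAE is defined in the same way between one treatment and the next. Protocol 9.1.1 has AEs recorded from consent onwards, and says that "during the screening period, adverse events will be assessed regardless of the administration of a pharmaceutical product". Up to 5 treatments are allowed (SAP 1.1), at least 12 weeks apart (Protocol 5.4.4.1).

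**The concern.** The trial's only objective is the long-term safety of repeated doses, and its main output is AE incidence overall and by cycle. Placing events in a phase is the only job of these imputations, so they should be judged on how well they do it.

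Rule (a) is evidently meant to be cautious: when the onset is uncertain, the event counts as treatment-emergent. But it is applied even where a recorded stop date shows that the event was over before the injection. Rule (c) uses a different anchor, and on one reading that anchor works in the opposite direction by taking uncertain events out of the TEAE count.

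**Working it through.** The plan states no figure on this point, so there is nothing to reproduce. The check applies the rules to dates.

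**Which injection rule (a) means.** Treatments are at least 12 weeks (84 days) apart and a month has at most 31 days, so a calendar month holds at most one injection. The day-missing branch is therefore unambiguous. A calendar year can hold all five. With the first on 20 January 2015 and steps of 84 days, the dates are 20 January, 14 April, 7 July, 29 September and 22 December. The year-only branch does not say which applies.

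**Rule (a) on worked dates**

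| Case | Known facts | Imputed onset | Result |
|---|---|---|---|
| Screening AE | Onset March 2015, stop 9 March, first injection 20 March | 20 March | After the stop; a resolved pre-treatment AE becomes a TEAE |
| Cycle 1 AE, true onset 3 April | Onset April 2015, stop 8 April, second injection 14 April | 14 April | After the stop; moved to cycle 2 |
| Same AE, only the year known, first injection of the year used | Stop 8 April | 20 January | Cycle 1, correct |
| Same AE, only the year known, last injection of the year used | Stop 8 April | 22 December | After the stop; moved to cycle 5 |

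Rule (a) cannot lose an overall TEAE. If the true onset is on or after the first injection, the imputed date is either that injection or something later.

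**Rule (c) under the two meanings of study entry**

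- *Consent or screening:* in a de novo patient the imputed onset is before the first treatment. The event is not a TEAE unless it worsens or becomes serious.
- *Day 1:* the imputed onset is the first treatment date. No TEAE is lost, and every such event goes to cycle 1.
- *Rollover patients:* the exit visit of Study 191622-101 serves as day 1 and there is no separate screening (Protocol 3), so the choice makes essentially no difference.

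**How often, among AEs that have an incomplete onset date.** The following are assumptions, not figures from the documents: five treatments 84 days apart, true onset uniform over 5 x 84 = 420 days, duration 3, 7 or 14 days, and day 1 spread evenly over a year. A simulation of 60,000 true post-treatment AEs gave:

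| Rule | Lost from overall TEAEs | Wrong cycle | Imputed onset after stop |
|---|---|---|---|
| (a), day missing | 0% | about 14% | about 8% |
| (a), only the year known | 0% | 61 to 71% | 7% (first injection of year) to 68% (last) |
| (c), entry = screening | 100%, barring worsening or seriousness | not applicable | not applicable |
| (c), entry = day 1 | 0% | about 80% | not applicable |

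Two of these can be checked by hand. For (a) with the day missing, each of the four later injections has on average (365/12 - 1)/2 = 14.7 days of its month before it, and 4 x 14.7 / 420 = 14%. For (c) at day 1, four of five equal cycles are wrong: 4/5 = 80%.

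With the day missing, every onset-after-stop case is also a wrong-cycle case. Falling back to the first of the month corrects it, because the previous injection is at least 84 days earlier. That leaves about 14% - 8% = 6% in the wrong cycle, which no stop date can resolve.

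**The case against.** Much can be said for the plan. Counting uncertain events as treatment-emergent is a recognised cautious convention. AEs are asked about at every visit with reference to the previous one (Protocol 9.1.1), so an onset with even the year unknown should be rare. Imputed dates do not enter days to onset, incomplete dates are listed as recorded, and the study plans no hypothesis testing unless otherwise specified (Protocol 7.3). All of this bears on the size of the effect and stands. It does not rescue rule (a): an event known to have ended before an injection is not uncertain with respect to that injection. Moving an event from one cycle to the next is not cautious either, because the overall count does not change.

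A reader might infer two stronger things that the documents do not support.

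- *That rule (c), by saying onset or stop, overwrites the known onset of an ongoing AE.* The sentence introducing rules (a) to (c) limits them to AEs whose onset is missing and imputes only what is missing. An AE with a known onset is outside their scope. The wording is loose, and a clarifying clause would help, but no known onset is replaced.
- *That rule (c) does bias TEAE incidence downward in de novo patients.* This depends on what study entry means. Protocol 9.1.1 and 9.3 start the study at informed consent, while Protocol 5.3 enrols both patient types at the day 1 visit. Parts of the SAP are also absent from the public text, including the section on pre-treatment AEs to which SAP 6.2 refers, and a definition may be there. This is an ambiguity, not a demonstrated bias.

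**Conclusion.** The point holds in two parts. Rule (a), as written, gives a wrong phase whenever a known stop date precedes an injection in the same imputation period and that injection is used. The error adds a resolved pre-treatment AE to the TEAEs or puts an event in a later cycle; it never removes an overall TEAE. When only the year is known, the rule also fails to say which of up to five injections it means. Rule (c) rests on a term that the readable text leaves undefined, and its two plausible meanings give opposite TEAE results for a de novo AE of unknown onset.

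The documents give no number or proportion of AEs with incomplete dates, so the effect on the tables is unknown and probably small. The percentages above apply only to such AEs and rest on the stated assumptions. The change is still worth making, because these tables are the main result and the repair is simple.

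**What to change.** - **Rule (a):** use the injection date only if it is not after the known stop date; otherwise use the start of the month or year.
- **Rule (a), only the year known:** state which injection applies. A workable choice is the latest injection in that year not after the known stop date, with a named default if the stop is also unknown. The choice matters. If the rule named the last injection of the year, the AE above that stopped on 8 April would fall back to 1 January, before the first injection on 20 January, and a true TEAE would be lost.
- **Rule (c):** replace the study entry date with the date of the first injection in Study 191622-105, unless a known stop date is earlier.
- **Both:** state that onset and stop are imputed separately and that a known date is never replaced.
- **Limit to declare:** the cycle of an AE with fully missing onset stays unknown. Assigning it to cycle 1 secures its overall TEAE status but not its cycle, and the SAP should call this a convention.

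The cost is a few lines of SAP text and derivation code. TEAE counts may move slightly in either direction.
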